phase. Informed by what stakeholders tell us, we will then work to build Relational Coordination within our hub-and-spoke network to deliver SBIRT-PM.

Within the VA, there are financial incentives for VISN-wide initiatives, such as the one proposed, that bring Veterans into VA care. The formula for funding each VISN is essentially a capitated model of payment per Veteran, called the Veterans Equitable Resource Allocation (VERA). Each additional patient in the New England VISN generates a mean of \$6500⁸⁷ (the median is considerably lower) and Veterans whose conditions are judged to be connected to their military service are, understandably, the highest priority Veterans for VA facilities to enroll. The VA as an organization depends on enrolling new Veterans as those from prior wars die or move to other regions.

Beyond having the potential to improve care for Veterans applying for compensation for MSD-related claims, to the extent SBIRT-PM results in new Veteran enrollment, it could increase revenue into VISN1 and its medical centers. Therefore, our proposal includes a budget impact analysis, with the prosaic but crucial information as to how SBIRT-PM impacts the VISN bottom line. We will determine the cost and cost-effectiveness of SBIRT-PM because these data provide evidence for SBIRT-PM's value.

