To comprehensively identify pain-related treatment delivered to study participants, we will validate and extend existing natural language search algorithms, using previously-described procedures, to identify current use of a comprehensive set of pain treatments including those *not covered by the existing algorithms*. Those modalities will be drawn from a review of modalities used by Veterans for pain treatment and those offered in VISN 1. Algorithm development will be informed by our prior experience with this study design. We will design algorithms to maximize positive predictive value (at the expense of sensitivity) to avoid the risk of including false positives that are not randomly distributed (e.g., refused treatment referrals). The NLP extraction target will be current use of the modality. Particular attention will be paid to excluding pain discussions that do not represent treatment because they were obtained in the course of routine medical history reviews. Algorithm development involves extracting relevant snippets that mention a particular pain treatment, establishing a valid classification system for current use of that pain treatment, and optimizing the machine learning algorithm to identify current use of that treatment.

Extracting relevant snippets: In brief, terms related to each of the pain treatments (i.e. therapy keywords) will be generated by the investigative team. For example, for physical therapy, terms might include “physical therapy,” “PT,” or “physical therapist.” A simple algorithm will identify these terms, along with the 10 preceding and 10 following words. By our observation, a 20-word window is sufficient to capture most of the relevant context, and also allows for fast review of multiple records. The algorithm will be modified using Boolean terms (e.g. physical NOT physical exam). We will refine the search terms and extract 20+ word snippets using the Voogo clinical data search engine.

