The counselor's explanation of the role of opioid medications paraphrases messages that primary care providers deliver to Veterans as part of [name] safe prescribing approach.⁹² The counselor explains that medications, including both opioid and non-opioid medicines, have an important place in some Veterans' pain treatment, and that Veterans benefit when pain medicines are prescribed and taken safely. The counselor reinforces the importance of taking opioid medicines as prescribed because there are risks of addiction and interactions with other substances (like alcohol). The counselor explains that judicious use of non-opioid medications improves pain treatment outcomes without these risks.

The counselor introduces the idea that non-pharmacological treatments can help manage pain, and explains what they are and how they work. These services may include: (1) treatment for the underlying ailment, (2) physical therapy (both at VA and as home exercise and stretching programs), (3) behavioral treatments like Cognitive Behavioral Therapy for chronic pain, (4) treatments for depression, PTSD, and/or other mental health problems that chronic pain may have aggravated, and (5) complementary and integrative health interventions available including chiropractor services, acupuncture and yoga.

Throughout these discussions, the counselor seeks opportunities to motivate the Veteran to engage in multi-modal pain care using a variety of MI consistent approaches. If the Veteran commits to engaging in pain management services, the counselor develops a plan with the Veteran to initiate this process. For Veterans not enrolled in VA services, the counselor explains the procedures to obtain eligibility for VA care.

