After the initial session, the counselor will have up to three 20-minute, mutually scheduled phone counseling sessions with the Veteran (about once per month for 12 weeks) to check on the Veteran's status in achieving the goals of the plan, and to gauge his or her continued motivation to receive pain treatment and reduce risky substance use, as indicated. An additional call during the 12-32-week period is permissible to remotivate veterans to engage in available pain and substance use services in view of any healthcare system changes that occurred (see response to COVID-19 section below). These calls may be informed by information the counselor has obtained from the PACT providers or information in the electronic health record (e.g., seeing if a consult was placed, reviewing progress notes indicating engagement with services). Twelve weeks allows time for the Veteran to work with the counselor to resolve barriers to service engagement, consider other treatment options, and sustain motivation for and engagement in pain management and ancillary services. Moreover, meta-analyses and "dose-response" studies^{93,94} have suggested the benefit of several follow-up telephone sessions.

Coordination with PACT Providers. The counselor will communicate with the PACT nurse case manager and primary care provider, or other point-of-contact about recommended pain treatment referrals primarily via the electronic health record. SBIRT-PM counselors will write progress notes that indicate the SBIRT-PM encounter and outcome of each session, including asking the provider to consider placing a consult for the Veteran's preferred services or discussing the Veteran's interest in services at the Veterans next scheduled appointment. SBIRT-PM counselors cannot place consults for services directly; only PACT providers or other licensed professionals working with the Veterans at their VAs can do so.

SBIRT-PM Clinician Supervision.

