5.2 Handling of Study Interventions

Study counseling sessions will be administered over the telephone in accordance with the counseling manual. After a counseling session has occurred, study counselors will place a note in the Veteran's electronic medical record indicating that a counseling session occurred and listing referrals the Veteran is interested in having placed.

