Data for the study are drawn from patient self-report, VA electronic medical records of VA and community care, and the C&P examination. Veterans requesting a Compensation & Pension evaluation for knee, shoulder, neck or back pain may or not be receiving services from the VA. Persons who get all their care outside of the VA will not have readily accessible medical records, while those persons who get some care in the VA but are sent out to community care for distinct services (such as non-pharmacological pain management) will have medical records of both types of care. In addition, those veterans who had not used any VA services prior to their C&P request may then enter VA care following their C&P exam and will have EMR available only in the follow-up period. The lack of EMR data of non-users of the VA will affect both the intervention or control arms of the study, and there is no reason to believe its effect will be differential.

Acknowledging the variability in availability of EMR information, all subjects will have self-reported and C&P data regarding service use as well as diagnoses. We will examine the concordance of self-reported and EMR-obtained information to estimate the impact of having no EMR data in the non-users of the VA. We will conduct a sensitivity analysis sub-setting the analyses only to those persons with available EMR (as well as self-reported and C&P data).

Cost-Effectiveness Analysis

The relative cost-effectiveness of SBIRT-PM will be assessed using both incremental cost-effectiveness ratios (ICERs) and cost-effectiveness acceptability curves (CEACs). ICERs and CEACs will be calculated from the provider (i.e., VISN and medical center) perspective. Using the cost estimates described in the Assessment subsection, we will calculate ICERs for minimal clinically important differences (MCID) between baseline and week-36 assessments in three primary outcomes: self-reported pain, risky alcohol use, and morphine-equivalent doses of opioid analgesic medication use.

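### Completeness of VA records may differ by arm, the 'available EMR' subset is undefined, and one-arm study notes and sessions are not excluded from service utilization

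*Combined protocol and SAP*

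**What the plan says.** Section 9.6 (Sources of data) acknowledges that Veterans cared for outside VA lack accessible records. It says this touches both arms and that "there is no reason to believe its effect will be differential". It also says that earlier non-users of VA may enter care after the C&P examination and "will have EMR available only in the follow-up period". The planned response is: "We will conduct a sensitivity analysis sub-setting the analyses only to those persons with available EMR". It gives no time point and no definition of available, and it does not say which analyses are repeated in the subset.

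Section 3 (data from the VA Electronic Health Record) states that every participant has a VHA record, but that service data are incomplete for Veterans not cared for at VA.

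On the intervention, Section 5.1 says: "For Veterans not enrolled in VA services, the counselor explains the procedures to obtain eligibility for VA care". Section 2.2 adds that "to the extent SBIRT-PM results in new Veteran enrollment, it could increase revenue into VISN1 and its medical centers".

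On documentation, Section 5.1 says "SBIRT-PM counselors will write progress notes that indicate the SBIRT-PM encounter and outcome of each session", and Section 5.2 describes a note in the medical record "listing referrals the Veteran is interested in having placed".

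On measurement, Section 9.6 (Analyses of NLP Algorithms) applies the NLP to participants' records. It counts a modality as used if self-report, stop codes or NLP is positive, on the ground that false positives should be rare. Utilization is a secondary outcome (Section 9.5.2) and a proposed mediator of both pain and substance use (Section 1.1).

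**The concern.** Three gaps bear on one family of results.

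First, the premise of no differential effect sits badly with an intervention that, in one arm, tells Veterans how to get into VA care. If more of that arm enters VA care, its records become more complete.

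Second, a subset defined by record availability is safe if availability is fixed before randomization. If records that first appear in follow-up qualify, the two arms of the subset may no longer be comparable, and the sensitivity analysis could reassure or alarm for the wrong reason.

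Third, counselor notes naming wanted treatments exist only in the SBIRT-PM arm, and so do the sessions. The questionnaire in Section 6.2.2 includes psychotherapy/counseling, and the Section 9.5.2 sum includes teaching about coping with pain. No statement keeps study notes or study sessions out of the count. Any such contamination would add apparent use in SBIRT-PM only, and so imitate the mechanism that the mediation analysis is meant to test.

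**Working it through.** The plan gives no figure on this point, so there is none to reproduce. The text comes first, then illustrations.

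**Text side by side.**
- Because everyone has a VHA record (Section 3), available cannot mean merely that a record exists. The issue is completeness.
- Section 9.6 itself calls records available when they begin in follow-up, so the post-randomization reading is a natural one. The schedule (Section 6.1) collects EHR service use at baseline, 12 and 36 weeks, so a baseline reading is equally possible.
- The any-of-three rule assumes that false positives are rare. Section 3 tunes the algorithms "to avoid the risk of including false positives that are not randomly distributed (e.g., refused treatment referrals". A wanted but unused referral is a close relative of a refused one.
- New reference snippets come from primary care notes (Section 3), so the PPV target of at least 90% would hardly test counselor notes.

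**Illustrations.** From the documents: d=.25 (Section 9.2) and 80% counseled in the pilot (Section 10.3.5). Every other input is assumed. Availability is treated as yes/no, which simplifies completeness.

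(a) *Subset defined in follow-up, applied to BPI severity with no true effect.* Let b be the share with VA care before randomization and r the share of the rest who enter by follow-up. Availability is a = b + (1−b)r. The share of the SBIRT-PM subset without a UC counterpart is (a1−a0)/a1, assuming nobody has records only under UC. The shift is that share times the difference between these extra entrants and the rest (0.25 to 0.5 SD, either sign).

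| b | r, UC / SBIRT-PM | a, UC / SBIRT-PM | Share | Shift (SD) | Relative to d=.25 |
|---|---|---|---|---|---|
| any | equal | equal | 0 | 0 | 0 |
| .70 | .30 / .40 | .79 / .82 | .03/.82 = .037 | .009 to .018 | 4% to 7% |
| .70 | .30 / .50 | .79 / .85 | .06/.85 = .071 | .018 to .035 | 7% to 14% |
| .50 | .30 / .40 | .65 / .70 | .05/.70 = .071 | .018 to .036 | 7% to 14% |
| .50 | .30 / .50 | .65 / .75 | .10/.75 = .133 | .033 to .067 | 13% to 27% |

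The shift is also 0 if the extra entrants resemble the rest. With a pre-randomization definition, availability is b in both arms in expectation, and this source of shift disappears.

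(b) *Detection gap with equal true use.* Difference = true use × availability gap × (1 − self-report sensitivity) × record sensitivity. With true use .50, record sensitivity .70 and a gap of .05 to .20:
- records alone: .50×.05×.70 = 1.8 points to .50×.20×.70 = 7.0 points;
- any-of-three, self-report sensitivity .60: multiply by .40, giving 0.7 to 2.8 points;
- any-of-three, self-report sensitivity .80: multiply by .20, giving 0.4 to 1.4 points.

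A gap of zero gives zero.

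(c) *Counselor notes.* Added any-use = .80 × f × (1 − base use), where f is the share of counseled Veterans wrongly flagged. f=0 gives 0. At base use .30, f=.02 gives 1.1 points and f=.05 gives 2.8. At base use .50 these are 0.8 and 2.0. If f were .20, the result would be 11.2 and 8.0, which shows how far the answer follows the assumed f.

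(d) *Does a PPV target carry over?* PPV = se×prev / [se×prev + (1−sp)(1−prev)]. With se=.70 and sp=.95, a prevalence of .40 gives .280/.310 = 90%; .20 gives .140/.180 = 78%; .10 gives .070/.115 = 61%. Section 3 relies partly on high prevalence to reach its target.

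(e) *Study sessions.* If every counseled Veteran's sessions counted as one modality, the summed count in SBIRT-PM would rise by .80 × 1 = 0.8. This is an upper bound for one modality, not an expectation.

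**The case against.** The safeguards are real. The NLP target is current use, and a wanted referral is future intent. Note type and temporal information are classifier features, and a modality that misses the PPV target falls back on self-report and codes. Section 9.6 tests missingness against intervention status, checks concordance of self-report with records, and cross-tabulates the sources. Under the any-of-three rule, a completeness gap alone matters little when self-report is sensitive. All of this stands and lowers the risk. It does not define the subset or say how study notes and sessions are treated, and neither the concordance check nor the cross-tabs are described as by arm.

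Stronger readings are tempting and are not supported:
- A reader might infer that SBIRT-PM does make records more complete. Section 2.2 is conditional, and the claim process can bring Veterans into VA care in both arms.
- A reader might infer that the sensitivity subset is biased. That needs the follow-up reading, and a baseline reading would be sound.
- A reader might infer that the NLP will count counselor notes as use. No passage shows this, nor does any say that study encounters carry stop codes.
- A reader might treat greater VA service use in SBIRT-PM as bias. Real use is the intended effect; only differential detection or false counting is at issue.

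**Conclusion.** The point holds in a limited form. The sentence denying a differential effect is not consistent with the protocol's own account of the intervention, the subset is undefined in a way that matters, and one-arm notes and sessions are left inside the utilization measure.

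The size is unknown. The illustrated ranges rest almost wholly on assumed inputs, and those in (a) to (c) include zero, so they show plausible order only. The overall direction is also unknown: a subset shift takes the sign of the difference between extra entrants and the rest, whereas false flags from one-arm notes could only add apparent use in SBIRT-PM.

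What is exposed is the EMR sensitivity analysis and the utilization outcome and mediator. The full ITT comparisons of BPI severity and ASSIST rest on self-report and are not affected. The changes are worth making before analysis because they are cheap; nothing here undermines the trial's main comparison.

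**What to change.** 1. Replace the sentence in Section 9.6 with a statement that record completeness may differ by arm, and report completeness by arm at baseline, 12 and 36 weeks.
2. Define the EMR sensitivity subset by VA care recorded before randomization, other than the C&P examination, and name the analyses repeated in it.
3. Exclude SBIRT-PM counselor notes, and any study encounters that carry codes, from NLP and stop-code extraction. State that study counseling sessions are not utilization in any source, including self-report. Any prompt to leave them out should be worded identically in both arms, so that the blinded research assistant learns nothing. Where answers already collected cannot be separated, show results with and without the counseling and coping-teaching items.
4. Keep the any-of-three rule, and break the planned concordance check and cross-tabs down by arm.

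The cost is a few sentences in the plan, a note-title or author filter, and extra columns in planned tables. The subset becomes smaller and leaves out Veterans new to VA care, and slightly fewer uses are detected. Counselors ask providers to consider consults, so referral wording can also appear in provider notes; that part would still depend on the classifier.

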1. STUDY OBJECTIVES

1.1 Primary Objective

Our main objective is to test the effectiveness and cost-effectiveness of SBIRT-PM, compared to UC, when delivered within a VISN1-wide hub-and-spoke network.

Objective 1: We will determine if SBIRT-PM is more effective than UC in reducing pain severity as measured by the Pain Severity subscale of the BPI (primary outcome). Secondary outcomes include non-pharmacological pain management service utilization, pain interference with life activities (BPI Interference Subscale), and overall health. Hypothesis: SBIRT-PM will be more effective than UC. We will test the degree to which non-pharmacological pain management service utilization mediates pain outcomes.

Objective 2: We will evaluate if SBIRT-PM, compared to UC, is more effective in reducing the number of substances categorized as requiring any intervention as measured by the ASSIST (primary outcome). Secondary outcomes will include the use severity measure for individual substances generated by the ASSIST, and nail clipping toxicology results for individual substances. Hypothesis: SBIRT-PM will be more effective than UC. We will separately test the degree to which non-pharmacological pain management service utilization and substance use service utilization mediates the effect of SBIRT-PM on substance use outcomes.

Objective 3: We will assess the cost-effectiveness of SBIRT-PM relative to UC. Hypothesis: SBIRT-PM will be cost-effective relative to UC across a range of possible values of decision makers' willingness-to-pay for minimal clinically important differences in pain severity and interference.

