- Characteristics of Musculoskeletal Disorders. We will determine the diagnostic group of MSD assigned to participants in the EHR by using ICD-9 or 10 codes. Major groups are back pain, neck pain, and osteoarthritis. Other categories will be combined as suggested by their frequency and co-occurrence with other MSD. These include non-traumatic joint disorders, osteoporosis, sprain and strain, traumatic joint disorder, spinal cord injury, fibromyalgia, rheumatoid arthritis, temporal mandibular disorder, lupus, gout, and MSD multimorbidity (more than one MSD diagnosed). The broad MSD groups will be considered as potential moderators of treatment effect in the analyses. In addition, compensation examiners complete a detailed, structured form, the Disability Benefits Questionnaire (DBQ), for each Veteran they evaluate. From these forms, we will extract structured notations of the examination findings. Finally, we will obtain the final percentage service-connection awarded from the Veterans Benefits Administration System (VBMS) after the determination, and delineate service-connected conditions.

Pain Measures:

- Brief Pain Inventory (BPI). The Brief Pain Inventory¹¹¹ (BPI) is a validated instrument to assess chronic non-cancer pain that yields two subscales. One measures pain severity (4 items on a 0-10 scale) and the other assesses pain interference with life activities (7 items on a 0-10 scale), both using a 24-hour recall period. BPI pain

severity will serve as our primary pain outcome for the trial; pain interference will serve as a secondary outcome. The BPI is a reliable measure and responsive to change.¹¹² The BPI is endorsed by the Initiative on Methods, Measurement, and Pain Assessment in Clinical Trials (IMMPACT) group¹¹³ as a preferred measure of pain-related functioning. IMMPACT recommendations have specified score changes that would represent a minimally clinically important difference (i.e., 30% reduction in pain severity and 1-point reduction in pain interference), which will be used in our cost analyses.¹¹⁴

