- Pain. Self-reported pain severity and interference will be measured by the Brief Pain Inventory (BPI). A MCID in pain severity will be a 30% reduction in ratings on this BPI subscale from baseline to week 36. The MCID for pain functioning will be a 1-point change in the BPI pain interference subscale. We have followed the guidelines Erin Krebs followed in the SPACE trial for selecting an MCID. She states in her group's 2018 JAMA report of the SPACE trial: "Following consensus guidelines, this trial used a 1-point difference as the MCID for BPI interference and BPI severity, and used a 30% reduction from baseline as MCID for moderate improvement."
- Substance Use. As noted earlier, the ASSIST categories represent what clinicians consider a clinically important difference, in that a difference the differences in risk category guide treatment. Therefore, we will consider a net decrease of one risk category (i.e. need for less overall treatment) across substances as the MCID.

The ICERs will measure the incremental cost of using SBIRT-PM to produce a MCID in each of the outcomes. We will conclude SBIRT-PM's cost-effectiveness for each outcome based on its ICER with respect to the threshold value placed by decision makers on the effect for that outcome. By using multiple outcomes, we can determine

the robustness of our cost-effectiveness findings and provide a more fine-grained cost-effectiveness analysis to address different priorities that stakeholders may have.^{186, 187}

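### The cost-effectiveness plan calls a 30% fall in BPI severity a minimal difference, but the source it says it follows gives 1 point for that and ties 30% to moderate improvement

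*Combined protocol and SAP*

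**What the plan says.** Objective 3 (section 1.1) frames the cost hypothesis in terms of "willingness-to-pay for minimal clinically important differences in pain severity and interference". Section 9.6, Cost-Effectiveness Analysis, expands the abbreviation in the same way: "we will calculate ICERs for minimal clinically important differences (MCID) between baseline and week-36 assessments".

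The pain bullet of section 9.6 then sets two thresholds. For severity: "A MCID in pain severity will be a 30% reduction in ratings on this BPI subscale from baseline to week 36". For interference: "The MCID for pain functioning will be a 1-point change in the BPI pain interference subscale". It says the choice follows the guidelines used in a cited opioid-strategy trial and reproduces a sentence from that trial's report. In that sentence "this trial used a 1-point difference as the MCID for BPI interference and BPI severity", and the trial "used a 30% reduction from baseline as MCID for moderate improvement".

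Section 6.2.2 (Brief Pain Inventory) gives a different basis. It says that consensus recommendations specify the changes that would "represent a minimally clinically important difference (i.e., 30% reduction in pain severity and 1-point reduction in pain interference", and that these will be used in the cost analyses.

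**The concern.** The plan names an authority for its MCID and prints that authority's words, but takes only half of them. For interference it uses the 1-point figure. For severity it passes over the 1-point figure in the same sentence, takes the criterion attached to moderate improvement, and keeps the word minimal.

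This matters for Objective 3, which rests on what decision makers would pay for a minimal difference. Someone who sets a value on the smallest worthwhile change in severity would have it applied to a change that the quoted trial ties to moderate improvement. The acceptability curves inherit the label, because their horizontal axis is the value placed on one MCID. The sensitivity analyses named for the cost work concern implementation parameters such as input costs. None of those named varies the MCID.

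A smaller point: section 9.6 gives the interference criterion as a change without a direction, where section 6.2.2 says reduction.

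**Working it through.** **Step 1. The texts side by side.**

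| Place | Severity | Interference | Stated basis | What 30% is called |
|---|---|---|---|---|
| 6.2.2, BPI | 30% reduction | 1-point reduction | consensus recommendations | minimal |
| 9.6, the plan's rule | 30% reduction | 1-point change | cited opioid-strategy trial | minimal (expansion in 9.6; Objective 3) |
| 9.6, quoted sentence | 1 point | 1 point | consensus guidelines, as reported by that trial | moderate improvement |

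The operating thresholds agree in 6.2.2 and 9.6. The meaning given to 30% does not.

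**Step 2. The 30% rule in BPI points.** Section 4.1 requires baseline severity of at least 4 on a 0–10 scale. The hurdle is 0.30 × baseline:

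| Baseline | 4 | 5 | 6 | 8 | 10 |
|---|---|---|---|---|---|
| 30% hurdle, points | 1.2 | 1.5 | 1.8 | 2.4 | 3.0 |

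No eligible participant has a hurdle at or below 1 point. The excess over 1 point runs from 20% (baseline 4) to 200% (baseline 10). The interference hurdle is flat.

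**Step 3. Effect on the ICER.** The plan gives no ICER figure to reproduce. I read the effect measure as the between-arm difference in the proportion reaching the MCID. Incremental cost is the same whichever threshold is used, so

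ICER(30%) / ICER(1 point) = [difference in responders at 1 point] / [difference in responders at 30%].

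From the plan: d = 0.25 (section 9.2). Assumed, because the documents do not give them: a normally distributed fall in severity, its SD, baseline severity, and the mean fall under usual care. The proportion responding is 1 − Φ((threshold − mean fall)/SD).

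Example: baseline fixed at 6 and SD 2, so the treatment adds 0.25 × 2 = 0.5 point.

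- Usual-care fall 0.5. At 1 point: 0.500 − 0.401 = 0.099. At 1.8 points: 0.345 − 0.258 = 0.087. Ratio 1.14.
- Usual-care fall 2.0. At 1 point: 0.773 − 0.691 = 0.082. At 1.8 points: 0.637 − 0.540 = 0.097. Ratio about 0.84.

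The ratio turns because the responder difference is largest when the threshold lies midway between the two arms' mean falls. In this example the two thresholds give equal differences when usual-care fall + 0.25 = (1 + 1.8)/2, that is, at a fall of 1.15 points.

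Next, baseline is spread as a normal distribution truncated to 4–10 (mean 5.0–6.0 and SD 1.4 before truncation, mean 5.6–6.2 after). SD of change is 1.6–2.0, and change is independent of baseline:

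| Assumed usual-care fall, points | ICER(30%) / ICER(1 point) |
|---|---|
| 0 | 1.20–1.51 |
| 0.5 | 1.11–1.29 |
| 1.0 | 1.03–1.10 |
| 1.5 | 0.93–0.95 |
| 2.0 | 0.79–0.87 |

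A wider grid with fixed baselines of 5–7, SDs of 1.5–2.5 and falls of 0–1 gives 1.00 to 1.94. The range is set by the assumptions.

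**The case against.** Four arguments count against the point.

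*The plan has a second basis for calling 30% minimal.* Section 6.2.2 cites consensus recommendations for exactly that. This stands. A reader might infer that 30% is simply mislabelled. The documents show only that two stated bases disagree, and the cited sources are not available here to settle it. The quoted sentence itself also applies the term MCID to 30%, though qualified as moderate improvement.

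*The 1-point figure may be a between-group difference.* If so, 30% is the only within-person criterion in the quoted sentence, and the ICERs need a within-person one. The wording allows this. But the plan itself uses the 1-point figure as a change from baseline to week 36 for interference, so it cannot easily refuse that reading for severity.

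*Each ICER has its own threshold value.* A reader might infer that the severity and interference ICERs become non-comparable. The plan makes no head-to-head comparison of the two, and the subscales measure different things even at 1 point each. What remains is that Objective 3 puts one label on both, and section 9.6 reads the outcomes together for robustness.

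*Any analyst would program the same severity rule.* True. The rule is explicit and consistent. The defect lies in what the result will be said to mean.

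**Conclusion.** The point holds as an internal conflict. Section 9.6 departs from the source it says it follows, and sections 6.2.2 and 9.6 give bases that disagree on whether a 30% fall is minimal or moderate. Relative to the quoted 1 point, the severity hurdle is stricter for every eligible participant, at 1.2 to 3.0 points. That rests only on the entry criterion and arithmetic.

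A reader might go on to infer that the 30% rule inflates the cost per severity MCID. The documents do not support this. With d = 0.25 and the assumptions shown, the ratio runs from about 1.5 with no usual-care improvement to about 0.8 with a 2-point improvement. The documents give no usual-care change, SD of change or baseline mean, so neither size nor direction can be claimed.

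The scope is the Objective 3 cost analysis. The BPI primary analysis and the sample size do not use the MCID.

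**What to change.** In section 9.6:

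- Keep the 30% severity ICER and acceptability curve, labelled as moderate improvement in line with the quoted sentence.
- Add a severity ICER and acceptability curve for a reduction of at least 1 point, labelled minimal.
- State the interference criterion as a reduction of at least 1 point, so that its direction matches section 6.2.2.

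Then align Objective 3 in section 1.1, the BPI text in 6.2.2, and the opening and pain bullet of the cost-effectiveness text in 9.6, so that one meaning of 30% runs through all of them.

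If the sponsor prefers to keep 30% as the minimal difference, it should justify that, correct the statement that the choice follows the quoted trial, and still report the 1-point severity ICER as a sensitivity analysis.

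BPI severity is already collected at baseline and week 36, so the cost is wording and one further set of ICER and acceptability-curve runs. The downside is one more set of results to present.
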